5. STUDY PATIENTS

5.1 Disposition of Patients

Subject disposition will be summarized for the total set of enrolled (ie, consented) subjects by study cohort. The subject disposition table will include:

- Number of enrolled subjects,
- Number of subjects in the safety, bone biopsy, and in the secondary efficacy populations
- Number and percentage of subjects completing the study and the number of those terminating early, and
- Number and percentage of subjects terminating early by reason for early termination.

For the presentation of the early terminations and reasons for early terminations, subjects will be counted under the last study visit completed prior to early termination.

5.2 Protocol Deviations

For cohorts 2 and 3, protocol deviations reported on the current protocol will be summarized by deviation type in a table and subject listing (as previously provided to the DSMB).

6. DEMOGRAPHIC AND OTHER BASELINE CHARACTERISTICS

Subject demographics at baseline will be summarized descriptively for each analysis population and cohort combination with appropriate descriptive statistics (number and percentages for categorical variables and mean, standard deviation, median, minimum and maximum for continuous variables). Demographic data will include: sex, ethnicity, race, age, weight, height, and body mass index (BMI).

7. EFFICACY EVALUATION

7.1 Handling of Dropouts or Missing Data

Missing data will not be initially imputed for the primary efficacy analyses. However, if the pattern of missing data in the primary efficacy analyses suggests the possibility of causing bias then as a secondary analysis, the primary analysis will be repeated using imputed values as described in section 7.4.3 below.

7.2 Efficacy Analysis

7.2.1 Primary Study Endpoints

The primary endpoints are changes in static and dynamic bone histomorphometry after 1 year, 2 years, and 4 years of hPTH therapy. These changes will be determined from antibiotic-labeled biopsies taken before and during hPTH therapy. The original protocol called for analyzing 7 bone markers of static and dynamic bone histomorphometry but the SAP has changed these to 8 bone markers of bone structure and bone remodeling. Analyses will be done on z-scores, when normative data are available. These are listed as follows:

7.2.1.1 *Bone Structure*

1. Cn.BV/TV: cancellous bone volume
2. Ct.Po.N: total number of cortical porosity per mm²

7.2.1.2 *Cancellous Bone Remodeling*

1. Cn.BFR/BS: Cancellous bone formation rate
2. Cn.MS/BS: Cancellous mineralizing surface (bone surface based)

7.2.1.3 *Endocortical Bone Remodeling*

1. Ec.BFR/BS: Endocortical bone formation rate
2. Ec.MS/BS: Endocortical mineralizing surface (bone surface based)

7.2.1.4 *Intracortical Bone Remodeling*

1. Ic.BFR/BS: Intracortical bone formation rate
2. Ic.MS/BS: Intracortical mineralizing surface (bone surface based)

7.2.2 Secondary Study Endpoints

7.2.2.1 *Static and dynamic bone histomorphometry (After 1, 2, and 4 years of hPTH) in secondary bone biomarkers*

Analyses relating to bone endpoints listed below will be done on z-scores, when normative data are available.

1. Bone Structure
 - a. Tb.Th: Trabecular Thickness
 - b. Tb.N: Trabecular Number
 - c. Tb.Sp: Trabecular Separation
 - d. Ct.Th: Average Thickness of Inner and Outer Cortices
 - e. Ct.Ar: Total Area of Inner and Outer Cortices
 - f. Ct.Po.Ar: Total Area of Cortical Porosity
2. Cancellous Bone Remodeling
 - a. Cn.O.Th: Osteoid Thickness
 - b. MAR: Bone Mineral Apposition Rate
 - c. OS/BS: Osteoid Surface / Bone Surface
 - d. ES/BS: Eroded Surface / Bone Surface
 - e. AjAR: Adjusted Apposition Rate
3. Endocortical bone remodeling
 - a. Ec.O.Th: Osteoid Thickness
 - b. Ec.MAR: Bone Mineral Apposition Rate
 - c. Ec.OS/BS: Osteoid Surface/Bone Surface
 - d. ES/BS: Eroded Surface / Bone Surface

- e. AjAR: Adjusted Apposition Rate
- 4. Intracortical bone remodeling
 - a. O.Th: Osteoid Thickness
 - b. MAR: Bone Mineral Apposition Rate
 - c. OS/BS: Osteoid Surface / Bone Surface
 - d. ES/BS: Eroded Surface / Bone Surface
 - e. AjAR: Adjusted Apposition Rate

7.2.2.2 *Changes in bone mineralization density (BMD) distribution will be assessed in bone biopsies by back-scattered electron imaging at 1, 2 and 4 years of hPTH therapy. The specific outcomes that will be measured include:*

Analyses will be done on z-scores, when normative data are available.

- 1. Spectral calcium-mean
- 2. Calcium-peak
- 3. Calcium-width
- 4. Calcium low
- 5. Calcium high

7.2.2.3 *Non-biopsy outcomes are being measured every 6 months (annually for some outcomes) over the 5 years of hPTH therapy. Changes from baseline in the following outcomes will be assessed:*

- 1. Biochemical markers of bone metabolism: osteocalcin, bone-specific alkaline phosphatase, collagen cross-linked N-telopeptide.
- 2. Serum and urine calcium; 1,25-OH₂-Vitamin D
- 3. Bone mineralization density assessed by DXA and quantitative CT including both raw and z-scores (based upon sex and age). These will include measures at the following anatomical sites
 - a. AP Spine
 - b. Lateral Spine

- c. Femoral Neck
- d. Total Hip
- e. 1/3 Radius
- f. Whole Body

The quantitative CT is limited to only the spine.

- 4. Nephrocalcinosis and Nephrolithiasis by ultrasound and CT
- 5. Fatigue Symptom Inventory
- 6. 6-Minute Walk Test
- 7. SF-36 Health Survey

7.3 Tertiary Outcome Measures

7.3.1 Changes in blood chemistries

Blood parameters include serum albumin, calcium, phosphorus, magnesium, sodium, potassium, chloride, total CO₂, creatinine glucose, and urea nitrogen.

7.3.2 Changes in fibroblast growth factor 23

This was assessed via fibroblast growth factor 23 (FGF23) analysis of the blood.

7.3.3 Changes in renal mineral handling and PTH sensitivity

Parameters for analysis include urine cAMP, creatinine, phosphorus, calcium, and pH.

7.4 Analysis Methods

All study endpoints used in analyses will be summarized in tables. Continuous endpoints will be summarized over time using n, mean \pm se, median, min, max. Endpoints requiring log-transformation will also be summarized over time using geometric means with their 95% confidence limits. Ordinal endpoints will be summarized using medians, min, max, and their 10th and 90th percentiles. Categorical endpoints will be summarized using number and percent in each category.

All efficacy analyses related to the bone biopsies will be performed on the Bone Biopsy Population. All efficacy analyses other than the bone biopsy related endpoints will be performed on the Secondary Efficacy Population.

For subjects who enter menopause during the study, any of their efficacy endpoints collected during or post-menopause will be excluded from the efficacy analyses, and will have such endpoints reported separately in the subject listings.

Unless otherwise stated, all statistical inference will be based on an alpha level of 0.05 with adjustments for multiple comparisons when needed as described below. Analyses will be made using SAS (SAS Institute, Cary, North Carolina), version 9.4 or later.

7.4.1 Primary Efficacy Analyses

Separate primary analyses will be performed for each of the eight primary bone structure and bone remodeling biopsy endpoints listed in section 7.2.1. Since the study was terminated early and is thus under-powered, no corrections for multiplicity will be made in the analyses of the 8 primary efficacy endpoints. For each of these primary bone biopsy endpoints, the primary analysis will test for differences with respect to the time of the biopsy (baseline, 1, 2, and 4 year). These endpoints will be analyzed using repeated measures mixed models with the bone biopsy endpoint as the dependent variable, the baseline value of the bone biopsy endpoint and study cohort as covariates, biopsy time (baseline, 1 year, 2 year, and 4 year) as the repeated measure, and subject as the random variable. The repeated measures will include a time-dependent covariate to adjust the baseline biopsy of Cohort 2 for the time delay between the baseline biopsy and the start of hPTH treatment. This covariate will adjust Cohort 2 for any possible further progression of disease occurring between the baseline biopsy measures and the start of hPTH therapy. An indicator variable in the statistical model will set the effects of this time-dependent covariate to zero for Cohort 3 and for the post-baseline biopsies of Cohort 2.

Pairwise contrasts between the bone biopsy times will be performed within the repeated measures analyses to compare the effects of the biopsy times on the bone biopsy endpoints. Because the sample size for 2-year and 4-year biopsies are reduced in size due to withdrawal and the early termination of the study, the 2-, and 4-year biopsies may be combined into one group provided their effects are qualitatively similar (i.e. the estimates of their effects are in the same direction). If the 2- and 4-year biopsies are qualitatively different then the 4-year biopsies may be dropped from the analysis due to its small sample size. The post hoc pairwise comparisons among the

biopsy time-points will be corrected for multiple comparisons using Fisher's protected LSD with Bonferroni corrections when the overall effect of biopsy year is not statistically significant.

Residual analysis will be used to confirm that model assumptions are reasonable. Log-transformations of the bone biopsy endpoints will be made if indicated by the residual analysis. The repeated measures will be fit using both a compound symmetry and an unstructured covariance structure. The better covariance structure will be selected as the model with the better Schwarz's Bayesian criterion. If the residual analyses of the statistical models indicate a failure to meet the assumptions of the repeated measures statistical models then other methods of statistical analysis including nonparametric analysis may be considered.

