799 are assessed every 6 months from baseline to 5 years of therapy. Thus, analyses of bone biopsy endpoints
800 involve both within-arm and between-arm comparisons at the 3 times, while all other analyses will utilize
801 standard repeated measures methods for longitudinal data.

802 These analyses will initially include all randomized subjects who remain evaluable for the endpoints,
803 including those eligible out of the subjects currently on conventional therapy plus the 36 newly enrolled
804 subjects. However, if covariate adjustment in analyses described below indicates that there are differences
805 between these strata, then the 3 strata will be analyzed separately. The subjects who were on HPTH under
806 the previous version of the protocol will be analyzed separately using similar analysis methods,
807 recognizing the limitations of the small sample size (≤ 8). Any subject who enters menopause prior to the
808 second bone biopsy will remain in the study and will undergo the second biopsy; however, the results will
809 be reported separately and not included in the data analyses of the randomized groups. It is felt that
810 reviewing the results from a menopausal woman anecdotally may give insight into possible treatment
811 effects in a menopausal sub-population. Data will be summarized graphically and in tabular form using
812 standard descriptive statistics for categorical and continuous measures, with appropriate consideration of
813 underlying distributional assumptions. All tests of significance will be two-tailed at the 0.05 level.

814 For the bone biopsy endpoints, paired t-tests will be used to test the hypotheses that the 1, 2, and 4-year
815 changes from baseline are significantly different from zero. One-way analysis of variance (ANOVA) will
816 be used to compare these differences to each other, with protected individual linear contrasts performed if

817 the overall F-test is significant. The effects of selected baseline covariates, including gender and
818 menopausal status, will be assessed using analysis of covariance (ANCOVA) in a sensitivity analysis.
819 Exploratory graphical methods will also be used to assess distributional assumptions and potential
820 differences in responses between the strata. Log-transformation of raw data or non-parametric test
821 alternatives may be considered if indicated by these exploratory analyses.

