846 either surrogate biomarkers for bone histomorphometric measures or as classifiers that could be used to
847 identify subjects more responsive to HPTH treatment.

848 Subjects and their data will be monitored closely throughout the study for safety; data will be submitted
849 regularly for DSMC review as described in Section 15. In addition, preliminary analyses using methods
850 described above may be performed when all evaluable subjects meet certain early milestones, for
851 example, after all subjects have completed their one year biopsy. These analyses will be designed to
852 evaluate early changes from baseline in primary and secondary measures after one year of HPTH
853 treatment and to assess the predictive values of selected secondary measures in relation to the primary
854 endpoints.

855 **10.2 Power Analysis**

856 Sample size calculations were based on 2 of the primary bone biopsy outcome measures, cancellous bone
857 mineralizing perimeter and bone formation rate, using preliminary data from the 5 previously enrolled
858 subjects who had biopsies at baseline and at 1 year of HPTH therapy. For mineralizing perimeter, the
859 mean (standard deviation) of the 1-year changes from baseline was 22 (7) %, and for bone formation rate
860 it was 0.23 (0.07) $\mu\text{m}^2/\text{mm}/\text{d}$. For design purposes, we assumed that a clinically meaningful change in
861 mineralizing perimeter from baseline to either 1, 2 or 4 years of therapy is 10% and will establish the
862 sample size required to detect a difference at least that large with adequate power. Using a two-tailed 0.05
863 level paired t-test, we found that 8 new subjects in each follow-up arm yielded 93% power to detect a
864 difference of 10% at any of the follow-up times. For bone formation rate, we assumed that a clinically
865 meaningful change from baseline is 0.10 $\mu\text{m}^2/\text{mm}/\text{d}$, which corresponds to an identical standardized
866 minimum detectable effect size of $0.10/0.07=1.4$ compared to $10/7=1.4$ for mineralizing perimeter. As a
867 result, 8 new subjects per arm will also yield 93% power to detect significant paired differences in bone
868 formation rate of 0.10 $\mu\text{m}^2/\text{mm}/\text{d}$.

869 A secondary analysis objective of the primary bone biopsy endpoints is to determine if there are
870 differences between the changes from baseline over time, using analysis of variance (ANOVA) for these

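### SAP 7.4.1 tests eight primary endpoints at 0.05 each without correction across them, and low power does not justify this; the chance of at least one false primary result is up to 34% if all eight nulls are true.

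*SAP*

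**What the plan says.** SAP 7.4.1: "Separate primary analyses will be performed for each of the eight primary bone structure and bone remodeling biopsy endpoints listed in section 7.2.1". Section 7.2.1 lists them: two structural measures, then bone formation rate and mineralizing surface in each of the cancellous, endocortical and intracortical envelopes.

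The general rule in SAP 7.4 is: "Unless otherwise stated, all statistical inference will be based on an alpha level of 0.05 with adjustments for multiple comparisons when needed". The SAP does not state sidedness; Protocol 10.1 does: "All tests of significance will be two-tailed at the 0.05 level".

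For the eight endpoints taken together, SAP 7.4.1 says "no corrections for multiplicity will be made in the analyses of the 8 primary efficacy endpoints". The reason precedes it: "Since the study was terminated early and is thus under-powered". The only correction in 7.4.1 works inside one endpoint, where comparisons among the "biopsy time-points will be corrected for multiple comparisons using Fisher's protected LSD with Bonferroni corrections", the Bonferroni step applying when the overall biopsy-time effect is not significant.

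Neither document names a lead endpoint, a testing order, or the number of endpoints that must succeed. SAP 7.4.2.3 also waives adjustment across the spectral calcium parameters, but there it calls the analyses more exploratory. The primary analyses carry no such label.

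**The concern.** The eight primary results will be read together, and a reader will give weight to whichever fall below 0.05. Without an order, a lead endpoint or an adjustment, the 0.05 level describes each test alone and not the set.

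The stated reason does not help. The false-positive rate of a valid 0.05 test does not depend on sample size, whereas the true-positive rate does. As numbers shrink, false positives make up more of what is declared significant. A small trial therefore has more need of a safeguard against chance findings.

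At stake is how the main publication words its primary findings. The estimates and raw p-values are not affected.

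**Working it through.** **Inputs.** Two-sided 0.05 per test (Protocol 10.1; SAP 7.4). Eight primary endpoints (SAP 7.2.1). Seven in the protocol (9.1). Smallest meaningful change in mineralizing perimeter 10%, SD 7%; pilot change 22% (SD 7%) in five subjects; 8 per arm for 93% power (Protocol 10.2). Of 19 new subjects treated, 8 gave an on-treatment biopsy (SAP 9).

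**1. The plan's own figure.** Paired t-test, n = 8, effect 10/7, df 7, noncentrality (10/7) × √8 = 4.04. Two-sided power at 0.05 is 93.1%, which agrees with the stated 93%. The documents give no familywise error rate to reproduce.

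**2. Familywise error, independent endpoints, all nulls true.**
- Eight endpoints: 1 − 0.95^8 = 33.7%.
- The protocol's seven: 1 − 0.95^7 = 30.2%.
- If only four of the eight nulls are true: 1 − 0.95^4 = 18.5%.

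**3. Correlated endpoints, all nulls true.** Eight two-sided z-tests, by simulation or numerical integration. The correlations are assumed.

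| Assumed correlation | Chance of at least one false result |
|---|---|
| Three pairs 0.9, all others 0 | 27.5% |
| Three pairs 0.9, all others 0.3 | 25% |
| Three pairs 0.9, all others 0.5 | 22% |
| Three pairs 0.9, all others 0.7 | 18% |
| All eight equal, 0.8 | 15.8% |
| All eight equal, 0.9 | 11.9% |

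F-tests with few error degrees of freedom give slightly higher values, for example 13% to 14% at equal correlation 0.9.

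**4. Does low power excuse the omission?** Suppose, for illustration, four true nulls and four real effects. Expected false positives are 4 × 0.05 = 0.20 whatever the power. At 93% power, expected true positives are 4 × 0.93 = 3.72, so the false share is 0.20/3.92 = 5%. At 30% power (three pairs at the minimum effect, step 5), they are 4 × 0.30 = 1.20 and the share is 0.20/1.40 = 14%.

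**5. What correction costs.** Paired-t power at 0.05 and at the strictest Holm level, 0.05/8 = 0.00625. The paired t-test stands in for the SAP's mixed model, and the pairs per comparison are assumed.

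| Effect | Pairs | Power at 0.05 | Power at 0.00625 |
|---|---|---|---|
| Pilot, 22/7 | 8 | over 99.9% | 99.97% |
| Pilot, 22/7 | 6 | over 99.9% | 97% |
| Pilot, 22/7 | 5 | 99.9% | 84% |
| Pilot, 22/7 | 4 | 98% | 52% |
| Pilot, 22/7 | 3 | 78% | 17% |
| Minimum, 10/7 | 8 | 93% | 60% |
| Minimum, 10/7 | 3 | 30% | 4% |

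The 8 new subjects with a second biopsy are spread over three biopsy times. Cohort 2 adds a number that the documents do not state, drawn from at most 10 (Protocol 10.3). Three or four pairs at a given time is therefore plausible.

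**The case against.** The SAP is open about what it does. It sets 0.05 per inference unless otherwise stated, and then states the exception. It runs separate analyses and defines no rule by which one success in eight makes the trial positive. The trial has a single treatment group, and Protocol 10.1 describes its aim as characterizing a response profile by exploratory and testing methods. All of this stands, and it limits the severity.

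Three stronger readings are tempting, and the documents support none of them.

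- A reader might infer that a promised 5% familywise rate has been broken. Neither document promises one.
- A reader might infer that the SAP removed a safeguard. The protocol had no correction across its seven endpoints either, so the maximum rose only from 30% to 34%.
- A reader might take about 21% as a lower limit for the error. It is not: plausible correlations give 18%, and very high ones 12%. That formation rate and mineralizing surface are near-duplicates is also an assumption. Every familywise figure for the eight endpoints taken together supposes that all eight nulls are true, which the pilot result makes unlikely for the two cancellous remodeling measures.

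It is also fair to object that correction is not nearly free. The reassuring power figures need six to eight pairs per comparison and come from a pilot on two of the eight endpoints.

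What the objection does not rescue is the stated reason. Openness about the omission does not make low power a justification for it, and the SAP does not call these analyses exploratory, as it does for the spectral calcium parameters.

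**Conclusion.** The concern holds in a limited form and should be fixed; it does not make the analysis unusable. Eight primary tests at 0.05 without correction give up to a 34% chance of at least one false primary result, if the endpoints are independent and all eight nulls are true. Under the assumed correlation patterns the figure is about 18% to 27%, or 12% to 16% if all eight are very highly correlated. Every case exceeds 5% by a factor of two or more, but the exact value cannot be known from the documents.

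The within-endpoint correction does not address this. Further flexibility is not counted in these figures: the 2- and 4-year biopsies may be combined, or the 4-year ones dropped, and the efficacy analyses are repeated in Cohort 3 alone (SAP 4 and 7.4.1).

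**What to change.** In SAP 7.4.1:

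1. Delete the under-powering rationale.
2. Keep the unadjusted p-values and add Holm-adjusted p-values for the eight overall biopsy-time tests in the combined Cohort 2 and 3 analysis.
3. Describe a result as a familywise-controlled primary finding only if it passes Holm.
4. Label the other primary p-values as exploratory, together with all pairwise contrasts for endpoints that do not pass. This matters because the SAP performs those contrasts even after a non-significant overall test.

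The work is a few sentences and one column in the combined-cohort primary table; the separate Cohort 2 and Cohort 3 tables in SAP 10 can stay unadjusted. No new data are needed.

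The real cost is that fewer endpoints will qualify. By the paired-t proxy the loss is small at the pilot effect with six to eight pairs. It is large with three or four pairs, or at the minimum effect even with eight. The estimates and unadjusted p-values stay in the report for readers who prefer them.
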